In both groups, patients will be receiving an oral beta-lactam antibiotic (for instance, amoxicillin, amoxicillin + clavulanic acid, cefixime, etc.) (see Background Antibacterial Therapy).

Patients will be able to start documentation in the patient diary only after receiving appropriate training.

In the diary, the subjects should daily document:

- Occurrence of bowel movements, specifying date/time for each bowel movement;
- Stool consistency (Bristol Stool Form Scale, BSFS) for each bowel movement;
- Intake of blinded IP (IMP/placebo);
- Intake of antibiotic;

|  |  |
|--|--|
|  | 

• Occurrence of gastrointestinal complaints (assessment of the severity of symptoms using a 5-point verbal scale [0 to 4]);

• Occurrence of pyrexia;

• Use of any drugs, other than the prescribed antibiotic therapy (indicating the name, strength and time of administration).

 
Visit 2 (Day 7 ± 2)
 
Intermediate Follow-up Visit
 
Procedures at Visit 2 for patients in each study group:
 

• Complaints reporting, medical history update;

• Reporting concomitant medications;

• Body weight measurements;

• Physical examination;

• Vital signs assessment;

• Complete blood count;

• Blood chemistry profile;

• Adverse event assessment;

• Evaluation of exclusion criteria;

• Review of patient diary;

• Dispensing of laboratory kit with the necessary supplies to collect stool samples (if necessary);

• Assessment of the adherence to study procedures (compliance with diary completion and study treatment);

• Assessment of diarrhea, if documented in the diary regarding its classification as AAD or non-AAD (according to investigator's judgment). If the results of stool samples analysis are not available during visit, the assessment will be done after the investigator receives the results from the laboratory.

 
Visit 3 (Day 15 ± 2)
 |
|--|--|

|  |  |
|--|--|

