#### ***5.2.4.2 Intermediate Follow-up Visit***

##### **Visit 2 (Day 7 ± 2)**

Procedures at Visit 2 in each study group:

- Complaints reporting, medical history update;
- Reporting concomitant medications;
- Body weight measurements;
- Physical examination;
- Vital signs assessment;
- Complete blood count;
- Blood chemistry profile;
- Adverse event recording;
- Evaluation of exclusion criteria;
- Dispensing of a laboratory kit with the necessary consumables for collecting stool samples (if necessary);
- Assessment of the adherence to study procedures (compliance with diary completion and study treatment);

- Diarrhea assessment based on patient diary entries and face-to-face interviews in relation to the use of antibiotics (AAD or non-AAD) as assessed by the investigator (in the absence of results of stool analysis at the time of the visit, the assessment is carried out after the investigator receives the results from the laboratory).

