#### **10.6 Missing, Suspect and Non-Amendable-To-Analysis Data Procedures**

During monitoring visits to the clinical center, Clinical Research Associates (Monitors) authorized by the Sponsor will analyze the CRF of the study subjects for the lack of necessary data. If there is any missing data in CRF and the relevant information is available in the source documentation, relevant queries to investigators shall be spelled out, as well as instructions for elimination of discrepancies. During check of the database, the Statistician, authorized by the Sponsor, and Managers for Data Control and Processing will determine whether there were any uncertain, missed, or non-amendable-to-analysis data, based on which queries to investigators can be defined. The investigators, if possible, eliminate the detected errors in CRF, and inform the Principal Investigator and authorized representatives of the Sponsor thereof. If the detected errors in the data cannot be eliminated after the completion of the patient's participation in the study, sensitivity of the resulting parameters to the presence of suspected data will be analyzed during the statistical analysis of the data. Information on missing, suspected and non-amendable-to-analysis data will be presented in the final clinical study report. For the primary endpoint, the method of filling in the missing values will be applied on the basis of the maximum likelihood estimation (MLE), if necessary [64]. For all other types of endpoints and other parameters, the analysis will be carried

out only using actually available information, without data fulfillment, which is associated with a short duration of the clinical study.

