**1. Dosing regimen of investigational medicinal products**

Did you take your research drug the way your doctor prescribed it?  Yes  No:

Comments \_\_\_\_\_ and  
complaints: \_\_\_\_\_

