**3. Occurrence of stool a day; consistency of stool**

Mark the time each chair episode occurred today and indicate the type of consistency (see Figure 1).

1. Time: \_\_\_\_\_  
Type 1234567

2. Time: \_\_\_\_\_  
Type 1234567

3. Time: \_\_\_\_\_  
Type 1234567

4. Time: \_\_\_\_\_  
Type 1234567

5. Time: \_\_\_\_\_  
Type 1234567

6. Time: \_\_\_\_\_  
Type 1234567

7. Time: \_\_\_\_\_  
Type 1234567

8. Time: \_\_\_\_\_  
Type 1234567

9. Time: \_\_\_\_\_  
Type 1234567

10. Time: \_\_\_\_\_  
Type 1234567

Comments \_\_\_\_\_ and  
complaints: \_\_\_\_\_

If you notice a loose stool or watery shapeless stool with a frequency of 3 or more times a day, you should call and inform your doctor. Your doctor will recommend the drugs approved for use in this study to eliminate symptoms of your condition.

Please remember that the decision to take additional drugs can only be made by a doctor.

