3.2. Procedure for missing, unanalyzable, and questionable data

During the monitoring visits to the study sites, the clinical study specialists (monitors) authorized by the Sponsor will analyze CRFs for data completeness. In the absence of data on CRFs and the availability of relevant information in the primary documentation, questions for investigators and regulations to address inconsistencies will be formulated. At the database check, the expert in statistics authorized by the Sponsor, the Data Control and Processing managers will analyze the study results for questionable, missing, and unanalyzable data, which might be the basis for the questions for investigators. If possible, the investigators will eliminate the errors identified in CRFs and inform the Principal Investigator and authorized representatives of the Sponsor hereof. In case the identified data errors cannot be eliminated after the completion of the patients' participation in the study, the analysis of the resulting parameter sensitivity to questionable data will be conducted in the statistical analysis. Information on missing, questionable, and unanalyzable data will be summarized in the final clinical study report. A method of filling in the missing data based on maximum likelihood estimation (MLE) for the primary endpoint will be applied if needed. The analysis of the rest of endpoint types and other parameters will be performed only on the basis of the available information without filling in the missing data in view of the short duration of the clinical study.

4. Study participants

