7.2. Analysis of secondary endpoints

The whole secondary efficiency analysis will be considered investigational, therefore multiplicity correction will not be performed; for test results, no formal capacity calculation will be provided.

Secondary efficiency points are classified into three groups:

1. Points characterizing the likelihood of a particular clinically significant event:
 - The occurrence rate of any diarrhea in the treatment group as compared to the placebo group;
 - The occurrence rate of C. difficile-associated AAD in the treatment group as compared to the placebo group;
 - The incidence of AAD not associated with C. difficile in the treatment group as compared to the placebo group;

- Frequency of gastrointestinal symptoms, including nausea, vomiting, flatulence, abdominal pain, and decreased appetite (according to the diary data), in the treatment group as compared to the placebo group;
- Number (share) of patients using standard symptomatic therapy to relieve symptoms of acute diarrhea in the treatment group as compared to the placebo group;
- The hospitalization rate in the treatment group as compared to the placebo group.

For these types of BKT, contingency tables 2×2 will be generated where the rows will show the groups, the columns will show the facts of the presence or absence of a particular event, the elements of the table are the patients included in the analysis. The contingency table data will be analyzed using Fisher's test (using the `fisher.test` function) or the chi-square test (using the `chisq.test` function) depending on the number of observations per cell (< 5 or ≥ 5).

2. Points characterizing the severity (or duration) of a particular clinical manifestation:

- Occurrence of bowel movements per day (according to the diary data) in the treatment group as compared to the placebo group;
- Duration of AAD (the time from the onset of AAD to the normalization of stool form according to BSS (types 1, 2, 3, and 4) and the presence of normal stool within 48 hours)) in the treatment group as compared to the placebo group;
- Duration of any diarrhea (time from diarrhea onset to normalization of stool form according to BSS (type 1, 2, 3, and 4) and presence of normal stool for 48 hours) in the treatment group as compared to the placebo group;
- Severity of the gastrointestinal symptoms, including nausea, vomiting, flatulence, abdominal pain, and decreased appetite (according to the diary data);

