- A number of days of using symptomatic therapy to relieve symptoms of acute diarrhea in the treatment group as compared to the placebo group.

Due to the obvious difference between the distribution of these indicators from the normal (they have a discrete distribution), the nonparametric Mann–Whitney–Wilcoxon test implemented in the `wilcox.test` function will be used for intergroup comparison.

3. Other secondary endpoints:

- Weight change at Visit 3 compared with Visit 1 in the placebo group as compared to the treatment group. This BKT can have a distribution close to normal. Accordingly, at the first stage, the normality of the distribution will be assessed (using the Shapiro–Wilk test implemented in the shapiro.test function), at the second stage, either the t-test (t.test function) or the Mann–Whitney–Wilcoxon test (wilcox.test function) will be used.
- Stool consistency change (according to Bristol Stool Scale) (according to the diary) in the treatment group as compared to the placebo group; any individual changes in stool consistency will be classified as improved/unchanged/worsened, and the difference between the groups will be analyzed using chi-square criterion (chisq.test function).

8. Safety analysis

Safety parameters will be evaluated at every planned or unscheduled visit.

The safety assessment will be based on the following indicators (between Visits 1 and 3) compared between the investigational medicinal product and placebo:

- Changes in the vital signs over time and the incidence of pathological abnormalities revealed during the physical examination will be summarized by the group; a comparison will be made between the groups using appropriate tests for quantitative and qualitative data.

The data will be checked for compliance with the normal distribution law using the Shapiro–Wilk test.

Intergroup comparison of secondary endpoints related to quantitative scales will be performed using Student's t-test for independent samples if the data correspond to the normal distribution law; otherwise, the Mann–Whitney U test will be applied to independent samples.

Intergroup comparisons of secondary endpoints related to categorical scales will be performed using Pearson's chi-square test if the number of points in each cell of the crosstab is ≥ 5 , or Fisher's exact test if at least one of the crosstab cells contains < 5 points.

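### The diary cannot record a stool-free day, and no rule says whether a blank stool item on an otherwise completed page is zero or missing

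*Protocol*

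**What the plan says.** **The form.** Item 3 on each daily page of Protocol Appendix 3 reads "Mark the time each chair episode occurred today and indicate the type of consistency" (the word 'chair' is evidently a translation of stool). Ten numbered lines for time and Bristol type follow, then a comments line. The protocol synopsis lists what patients document daily, including "Occurrence of bowel movements, specifying date/time for each bowel movement"; it gives no instruction for a day on which none occurs.

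**The other items on the page.** Study drug ("Did you take your research drug the way your doctor prescribed it"), antibiotic, each of five gastrointestinal symptoms and symptomatic therapy take Yes/No answers. Body temperature takes a number. Each of these can show that the patient considered the question and answered it.

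**The endpoint.** SAP 7.2 lists "Occurrence of bowel movements per day (according to the diary data) in the treatment group as compared to the placebo group" among the severity and duration endpoints and states that "the nonparametric Mann–Whitney–Wilcoxon test implemented in the `wilcox.test` function will be used for intergroup comparison". All secondary analyses are declared investigational, without multiplicity correction.

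**The missing-data rule.** For every endpoint except the primary, SAP 3.2 says that analysis "will be performed only on the basis of the available information without filling in the missing data". Protocol 10.6 has the same rule: the analysis is carried "out only using actually available information, without data fulfillment, which is associated with a short duration of the clinical study". Neither section defines when a diary day counts as missing.

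**The checks.** Visits 2 and 3 include "Assessment of the adherence to study procedures (compliance with diary completion and study treatment"), and Protocol 5.2.3.2.6 has the investigator evaluate daily bowel movements from the diary.

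**The concern.** Item 3 is the only structured daily item without a way to enter a negative. A patient who had no stool and a patient who passed over the item hand in the same blank. The coding is then left to whoever enters or programs the data, and each of the two natural choices is wrong for some of the blanks. An analyst cannot undo this later, because the information was never collected.

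At stake are the stool-frequency comparison, the dating of the end of a diarrhea episode (which needs normal stool over a 48-hour window), and the number of missing values that the SAP table layouts require. To a lesser degree, a skipped item could also be read as a day without diarrhea.

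**Working it through.** **1. The plan's own figure.** The documents give no number for stool frequency. The only design calculation is for AAD: ((1.960 + 0.842)/0.11)² × [0.15×0.85 + 0.26×0.74] = 207.51, rounded up to 208 per group, and 208/0.80 = 260 randomized per group. It reproduces and does not depend on this point.

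**2. What a page can show.**

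| Other items | Item 3 | Can be concluded |
|---|---|---|
| filled | entries | stool count known |
| blank | blank | page not completed |
| filled | blank | zero stools, or item skipped |

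The ambiguity is confined to the last row, which is also exactly how a genuine stool-free day appears.

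**3. Inputs for the size.** z = share of stool-free days, m = mean stools on days with at least one stool, u = share of days on which item 3 was skipped. None is in the documents, so all are assumed. Skipping is taken to be unrelated to the count. The true mean is (1−z)m.

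**4. Blank coded as missing.** The observed mean is m, so the relative error is 1/(1−z) − 1.
- z = 5%: 1/0.95 − 1 = +5.3%
- z = 10%: 1/0.90 − 1 = +11.1%
- z = 20%: 1/0.80 − 1 = +25.0%

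**5. Blank coded as 0.** The observed mean is (1−u)(1−z)m, so the relative error is −u: −5% at u = 5%, −10% at u = 10%. No zero day is lost, but every skipped item becomes a false zero.

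**6. Difference between arms.** The direction depends on how the arms differ and on the coding.
- Blank = missing, z of 20% against 10%, m = 1.3 in both: the true difference is 1.04 − 1.17 = −0.13 and the observed difference is 1.3 − 1.3 = 0. The effect disappears.
- Blank = missing, z = 10% in both, m of 1.2 against 1.5: the true difference is 1.08 − 1.35 = −0.27 and the observed difference is −0.30. The effect is 11% too large.
- Blank = 0, true mean 1.35 in both, u of 5% against 10%: 1.2825 − 1.215 = 0.0675. A difference appears where there is none.

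These are differences in means. The SAP tests ranks, and neither document says how a patient's daily counts become one value, so the figures show direction and order of size, not the effect on the p-value.

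**7. Other outputs.** In the duration endpoints, a blank day inside the 48-hour window could be stool-free or unrecorded, so the end date of the episode is open. The Missed row in SAP Appendix 1, Table No. 1, cannot be filled for daily stool counts without a coding rule.

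**The case against.** The strongest reply is that nothing in the SAP produces the loss of zero days. SAP 3.2 and Protocol 10.6 forbid filling in missing data, but they do not class a blank stool item as missing, and entering 0 for a blank on a completed page would not be imputation. That stands. A reader might infer that the available-data rule necessarily drops zero days, biases stool frequency upward and shrinks the treatment difference; the documents do not support this. For example, Poisson counts with means 1.3 and 1.5 would turn a true difference of 0.20 into 0.144 on stool days only, 28% smaller. But no section states a Poisson model or an average over stool days, and step 6 shows that the difference can also grow.

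A second reply is that AAD does not rest on the diary alone. Classification at Visits 2 and 3 also uses face-to-face interviews (Protocol 5.2.4.2 and 5.2.4.3). Patients with diarrhea must contact the site and collect stool samples (synopsis and Appendix 2), and item 3 itself tells them to call the doctor at three or more loose stools. A true stool-free day is also correctly a non-diarrhea day. This stands as well, so a reader should not infer that missing and negative AAD outcomes are generally inseparable.

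A third reply is that diary review, compliance checks and data queries are already planned, that item 3 has a comments line, and that the eCRF, which is not among the documents, may accept a zero. This stands only in part. None of the planned checks has a stated rule for a blank stool section. With Visit 2 as early as Day 5 and Visit 3 as late as Day 17, a query may rely on recall over as much as 17 − 5 = 12 days. An eCRF field cannot supply what the paper source does not hold.

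**Conclusion.** The point holds as a gap in data collection together with a missing coding rule. Item 3 cannot record zero, and for a blank stool item on an otherwise completed page the plan does not choose between zero and missing.

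The size depends on assumed shares. Mean stools per day is overstated by about 5% to 25% for stool-free shares of 5% to 20% if blanks are missing, and understated by 5% to 10% for skipped shares of 5% to 10% if blanks are zero. The sign of any between-arm bias cannot be stated.

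The consequences are modest: an exploratory frequency endpoint, the closing window of the two duration endpoints, and the reported count of missing values. For AAD what remains is a small risk that a skipped item is taken as no diarrhea. Sample size and the primary test are unaffected. The assessment of the form rests on extracted text; figure placeholders appear in items 4 and 5 of the diary pages but none in item 3.

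**What to change.** Add a 'No bowel movement today' tick box to item 3 on every diary page, with a matching eCRF field. State in SAP 3.2 and 7.2 that a ticked day counts as 0 stools and not diarrhea, and that a day with neither a tick nor any stool entry is missing. In the same place, state how daily counts are reduced to one value per patient. Let the diary review already planned at Visits 2 and 3 query stool sections that have neither tick nor entry.

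The cost is one box, one eCRF field and a short SAP addition. The downside is a few more diary queries.

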#### 4. Body temperature

[figure not shown]
Measure the body temperature in the axillary cavity with a mercury thermometer and record the result: \_\_\_\_\_

Comments \_\_\_\_\_ and  
complaints: \_\_\_\_\_

[figure not shown]
#### 5. Gastrointestinal symptoms

Mark the occurrence of each of these symptoms during the day and rate the severity of symptoms on a 5-point verbal scale (0 to 4):

[figure not shown]
Nausea:  Yes  No

[figure not shown]
Vomiting:  Yes  No

[figure not shown]
Flatulence:  Yes  No

Abdominal pain:  Yes  No

Decreased appetite:  Yes  No

Comments \_\_\_\_\_ and  
complaints: \_\_\_\_\_

**6. Symptomatic therapy**

Have you taken any medication to eliminate symptoms of the underlying disease and/or symptoms of diarrhea?  Yes  No:

If yes, provide the name, dose, time and frequency of the medication(s):

\_\_\_\_\_  
\_\_\_\_\_  
\_\_\_\_\_

**Filled by the patient:** Day No. 2

Date \_\_/\_\_/\_\_\_\_

**1. Dosing regimen of investigational medicinal products**

Did you take your research drug the way your doctor prescribed it?  Yes  No:

Comments \_\_\_\_\_ and

complaints: \_\_\_\_\_

**2. Antibacterial therapy regimen**

Did you take the antibiotic the way your doctor prescribed it?  Yes  No:

Comments \_\_\_\_\_ and

complaints: \_\_\_\_\_

**3. Occurrence of stool a day; consistency of stool**

Mark the time each chair episode occurred today and indicate the type of consistency (see Figure 1).

1. Time: \_\_\_\_\_

Type 1234567

2. Time: \_\_\_\_\_

Type 1234567

3. Time: \_\_\_\_\_

Type 1234567

4. Time: \_\_\_\_\_

Type 1234567

5. Time: \_\_\_\_\_

Type 1234567

6. Time: \_\_\_\_\_

Type 1234567

7. Time: \_\_\_\_\_

Type 1234567

8. Time: \_\_\_\_\_

Type 1234567

9. Time: \_\_\_\_\_

Type 1234567

10. Time: \_\_\_\_\_

Type 1234567

Comments \_\_\_\_\_ and

complaints: \_\_\_\_\_

If you notice a loose stool or watery shapeless stool with a frequency of 3 or more times a day, you should call and inform your doctor. Your doctor will recommend the drugs approved for use in this study to eliminate symptoms of your condition.

Please remember that the decision to take additional drugs can only be made by a doctor.

**4. Body temperature**

[figure not shown]
Measure the body temperature in the axillary cavity with a mercury thermometer and record the result: \_\_\_\_\_

Comments \_\_\_\_\_ and  
complaints: \_\_\_\_\_

[figure not shown]
**5. Gastrointestinal symptoms**

Mark the occurrence of each of these symptoms during the day and rate the severity of symptoms on a 5-point verbal scale (0 to 4):

[figure not shown]
Nausea:  Yes  No

[figure not shown]
Vomiting:  Yes  No

[figure not shown]
Flatulence:  Yes  No

Abdominal pain:  Yes  No

Decreased appetite:  Yes  No

**6. Symptomatic therapy**

Have you taken any medication to eliminate symptoms of the underlying disease and/or symptoms of diarrhea?  Yes  No:

If yes, provide the name, dose, time and frequency of the medication(s):

---

---

---

---

---

**Filled by the patient:** Day No. 3

Date \_\_/\_\_/\_\_\_\_

**1. Dosing regimen of investigational medicinal products**

Did you take your research drug the way your doctor prescribed it?  Yes  No:

Comments \_\_\_\_\_ and  
complaints: \_\_\_\_\_

**2. Antibacterial therapy regimen**

Did you take the antibiotic the way your doctor prescribed it?  Yes  No:

Comments \_\_\_\_\_ and  
complaints: \_\_\_\_\_

